1.0 Background of the Surveillance

Since the amount of leuprorelin acetate administered in a single dose of Leuplin PRO for Injection Kit 22.5 mg (hereinafter referred to as Leuplin PRO) is as high as twice that of Leuplin SR for Injection Kit 11.25 mg (hereinafter referred to as Leuplin SR), and the time profile of serum leuprorelin concentration after administration differs between the two formulations, a special drug use surveillance (hereinafter referred to as the surveillance) is planned to evaluate potential effects of the differences on the safety.

This surveillance will be conducted in compliance with the ministerial ordinance on Good Post-Marketing Study Practice (GPSP) and related regulatory requirements.

2.0 Objectives

To investigate the safety of Leuplin PRO in patients with premenopausal breast cancer in routine clinical settings in order to evaluate potential effects of differences between Leuplin PRO and Leuplin SR, including the higher amount administered in a single dose and differences in time profile of serum drug concentration after administration, on the safety

3.0 Planned Sample Size and Rationale

3.1 Planned Sample Size

300 patients

3.2 Rationale

To evaluate potential effects of differences between Leuplin PRO and Leuplin SR, that is, difference amounts of leuprorelin acetate administered in a single dose and different time profiles of serum drug concentration after administration, on the safety, it was decided to investigate the occurrence of injection site reaction and other adverse drug reactions (ADRs) with an incidence of 1% or higher, including the time of onset, incidence, and seriousness.

The sample size of 300 patients was determined to detect ADRs with an incidence of 1% or higher at a probability of 95% or higher.

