8.0 Planned Surveillance Period

Surveillance period: From March 2016 to 31 August 2017

Patient registration period: From April 2016 to 28 February 2017^{Note)}

^{Note)} Patient registration (entry into [CCI]) will not be accepted on 1 March 2018 onwards even if Leuplin PRO is administered by 28 February 2018.

If the number of patients enrolled in the surveillance reaches the planned sample size before 28 February 2018, acceptance of registration will be terminated before the end of the patient registration period. If the patient registration period is shortened, the surveillance period will be changed accordingly.

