10.2 Analysis Sets

The analysis set is patients included in safety evaluation.

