1.1 List of Terms and Abbreviations

- Leuplin PRO: Leuplin PRO for Injection Kit 22.5 mg is abbreviated as Leuplin PRO.
- Adverse drug reaction (ADR), etc.: ADR, etc. is an abbreviation of ADR/infection. ADRs, etc. refer to all adverse events (AEs) other than those assessed by the investigator to be not related to Leuplin PRO. In this document, “adverse drug reactions/infections” is used in titles, and “ADR, etc.” is used in the text and tables.
- Serious adverse event (SAE): A SAE is an adverse event assessed by the investigator to be serious. Events included in the MedDRA code list in Takeda Medically Significant AE List will be handled as serious even if assessed by the investigator to be not serious.
- Causal relationship: An event assessed as not related to Leuplin PRO will be handled as “not related.” Events not unrelated to Leuplin PRO in the text and tables refer to all events other than those assessed as not related to Leuplin PRO.
- Summary statistics: Collective term for number of patients, mean, standard deviation, maximum, minimum, and quartiles
- Patient with no CRF collected: Enrolled patient for whom the CRF has not been collected
- Patient with the CRF collected: Enrolled patient for whom the CRF has been collected
- Finalized patient: Patient for whom the CRF has been collected and finalized at least once by data lock point
- Non-finalized patient: Patient for whom the CRF has been collected, but has not been finalized by data lock point
- Age: If the month and day of starting Leuplin PRO treatment is smaller than the month and day of birth, age will be calculated as year of starting Leuplin PRO treatment - year of birth - 1. If the month and day of starting Leuplin PRO treatment is equal to or greater than the month and day of birth, age will be calculated as year of starting Leuplin PRO treatment - year of birth. If the day of birth is unknown, 1 will be used for calculation.
- Time from diagnosis of premenopausal breast cancer to patient registration (months):
 - Actual number (units: month) = (“date of patient registration” - “date of diagnosis” + 1)/30.44
- BMI (kg/m²): Calculated as body weight (kg)/height (m)² (displayed to one decimal place by rounding)

- Induration: AE with “induration” selected for “Specific symptom (multiple answers allowed)” in the column of [Adverse event: Injection site reaction] in the CRF

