1.2 Analysis Sets

The analysis set in this surveillance is safety population. This analysis set is defined as described below.

- Safety population

In this document, the safety population is defined as all Leuplin PRO-treated patients evaluable for safety with no major protocol violation. Patients for whom the CRF has been collected will be excluded from the safety population if any of the following criteria is met:

- Not treated with Leuplin PRO
- Treatment before the contract period
- Registration 15 days or more after Leuplin PRO treatment
- It is unknown whether the patient experienced an AE
- Three-month depot administered

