2.1 Disposition of Patients

Patients included All enrolled patients (enrolled patients)

in analysis:

Analysis items: Enrolled patients

Number of surveillance medical institutions

Patients with no CRF collected

Reason for failure to collect

[Transfer of the investigator, medical reason for the investigator, other]

Patients with the CRF collected

Non-finalized patients

Finalized patients

Patients excluded from safety evaluation*

Reason for exclusion (multiple tabulation)

[Not treated with Leuplin PRO, treatment before the contract period, registration 15 days or more after Leuplin PRO treatment, it is unknown whether the patient experienced an AE, 3-month depot administered]

Patients included in safety evaluation*

Analysis methods:

For the aforementioned analysis items, analysis will be performed as described below, and a patient composition diagram will be prepared.

For enrolled patients, the number of surveillance medical institutions will also be calculated. One medical institution with different departments will be counted as one medical institution.

* Patients included in safety evaluation refer to the safety population, and patients excluded from safety evaluation refer to patients excluded from the safety population (finalized patients excluded from the safety population here).

(1) Frequency tabulation

3 Patient Baseline Characteristics

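### Does the 95% chance of seeing a 1% ADR fail because the 300 patients are counted at enrolment and not in the safety population?

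*Protocol*

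**What the plan says.** Protocol 3.1 sets the planned size at 300 patients, and 3.2 gives the reason: "The sample size of 300 patients was determined to detect ADRs with an incidence of 1% or higher at a probability of 95% or higher". It does not say whether these are enrolled or evaluable patients.

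Protocol 8.0 ties early closure of registration to enrolment: "If the number of patients enrolled in the surveillance reaches the planned sample size before 28 February 2018", then "acceptance of registration will be terminated before the end of the patient registration period".

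The analysis uses a different count. Protocol 10.2 says: "The analysis set is patients included in safety evaluation". The footnote to SAP 2.1 equates the two terms: "Patients included in safety evaluation refer to the safety population". SAP 5.1.2 uses that number as the denominator for the proportion of patients with an ADR.

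The SAP describes several ways in which an enrolled patient may not reach that set:

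- SAP 2.1 has a line for "Patients with no CRF collected".
- SAP 1.1 defines a non-finalized patient: "Patient for whom the CRF has been collected, but has not been finalized by data lock point".
- SAP 1.2 adds: "Patients for whom the CRF has been collected will be excluded from the safety population if any of the following criteria is met". Five criteria follow: not treated with the product, treated before the contract period, registered 15 or more days after treatment, unknown whether an AE occurred, and given the three-month depot.

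Neither document states an allowance for such losses.

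**The concern.** The 95% statement is the only quantitative property the protocol claims, and it is the stated basis for the sample size. It is worded as a threshold, so it either holds or does not for a given number of patients. The number planned is one more than the minimum. If registration closes at exactly 300 and two patients are then left out of the safety population, the threshold is missed.

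The natural reading is that the sponsor sized the surveillance on enrolment, overlooked the drop from enrolled to analysed, and might repeat the 95% claim in the report for a population in which it no longer holds. What would be at stake is the accuracy of that one sentence, which readers use to judge what the absence of a given ADR among the patients observed can rule out.

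**Working it through.** **Inputs.** Planned size 300 (protocol 3.1). Incidence 1% and target probability 95% (protocol 3.2). Counting at enrolment (protocol 8.0). Analysis in the safety population (protocol 10.2, SAP 1.2). Loss rate: not given in either document.

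**The plan's own figure.** Read detection as at least one case. The probability is then 1 − (1 − p)^n.

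- n = 300, p = 0.01: 1 − 0.99^300 = 95.10%. The stated figure reproduces.
- Requiring at least two cases would give 80.2% at n = 300, so at least one case is the reading that fits.

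**Smallest n that meets 95%.** ln(0.05)/ln(0.99) = 298.07, rounded up to 299. From 300, the margin is one patient (1/300 = 0.33%).

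**If exactly 300 are enrolled and some are lost.** The last column is the incidence that would be seen at least once with 95% probability, 1 − 0.05^(1/n).

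| Lost | n analysed | Probability of seeing a 1% ADR | Incidence seen with 95% probability |
|---|---|---|---|
| 0 | 300 | 95.10% | 0.994% |
| 1 | 299 | 95.05% | 0.997% |
| 2 | 298 | 94.996% | 1.0002% |
| 3 | 297 | 94.95% | 1.004% |
| 5 | 295 | 94.84% | 1.010% |
| 10 | 290 | 94.58% | 1.028% |
| 15 (assumed 5%) | 285 | 94.30% | 1.046% |
| 30 (assumed 10%) | 270 | 93.37% | 1.103% |

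The last two rows rest on assumed loss rates and show the range only.

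**Size of the shortfall.** With two lost it is 95 − 94.996 = 0.004 percentage points. With ten lost it is 95 − 94.58 = 0.42 points. With an assumed 10% loss it is 95 − 93.37 = 1.63 points. SAP 1.3 shows percentages to two decimals for AE and ADR proportions and to one decimal otherwise. At either precision, 94.996% prints as 95.00% or 95.0%.

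**If enrolment exceeds 300.** Section 8.0 ends registration on reaching the planned size but does not cap it at that number. The tolerated loss is N − 299. For 305 enrolled that is 6 (6/305 = 1.97%); for 310 it is 11 (11/310 = 3.55%).

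**How readily patients are lost.**

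- Registration follows dosing (protocol 7.3), so a registered patient should already have been treated.
- The administration date is a registration item (protocol 9.1), so treatment before the contract period and late registration can be checked at entry.
- Discontinuation of observation is tabulated within the safety population (SAP 4.3), so it does not by itself remove a patient.
- Non-finalization is not among the SAP 1.2 criteria. That it removes a patient is inferred from the layout and footnote of SAP 2.1.

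Any of these categories may turn out to be empty.

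**The case for a change.** The strongest case for a change runs as follows. A claim of at least 95% is a threshold, and it should name the number of patients on which it depends. The SAP itself provides for the enrolled and analysed sets to differ, by seven routes, yet the rationale leaves a margin of one patient. The 3.2 wording and the enrolment-based stop are the same in every protocol version supplied. A remedy would be cheap: one conditional sentence in 3.2, and a line giving 1 − 0.99^n for the actual safety population.

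Much of this stands. The arithmetic is right, the two counts differ, and no allowance is stated. What does not stand is the step from there to a defect in the plan. Section 3.2 explains how a planned number was chosen and is correct for the number it names; it makes no claim about the safety population eventually achieved. The SAP has no sample-size section and never states the 95% figure, so it contains nothing to correct. That the report would repeat the figure for a smaller population is conjecture.

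**Conclusion.** No change to the plan is needed. The 3.2 figure is correct for 300 evaluable patients and needs at least 299. The gap between enrolled and evaluable patients is an unstated condition. The documents do not show that the surveillance misses its target, because they give no loss rate and allow enrolment above 300.

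If exactly 300 were enrolled and ten were lost, the probability would be about 94.6% instead of 95%, and the incidence seen with 95% probability would be 1.03% instead of 1.00%. It would take about 35 losses (12%) to bring the probability down to about 93%. No planning decision turns on differences of this size.

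Writing the condition down would also gain little now. The SAP is dated 4 April 2019, after both registration end dates that appear in protocol 8.0 (28 February 2017 and 28 February 2018), so enrolment can no longer be adjusted. The outputs are descriptive counts and proportions that do not depend on the 95% figure. Protocol 10.3 and SAP 2.1 already require tabulation of patients enrolled, CRFs collected, and patients included and excluded with reasons. A reader will have the actual n and can put it into 1 − 0.99^n. An author who wishes to repeat the 95% figure in the report would sensibly do the same.

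This conclusion assumes that detection means at least one case and that losses are modest. A large loss would show in the disposition table.

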4.0 Surveillance Population

Patients with premenopausal breast cancer will be included in the surveillance. Patients should not meet the exclusion criterion listed below. Refer to the Precautions section of the package insert.

<Exclusion criteria>

Patients who meet the following criterion will not be included:

- A history of hypersensitivity to any of the ingredients of Leuplin PRO or synthetic luteinizing hormone-releasing hormone (LH-RH) or LH-RH derivatives
- Pregnant or potentially pregnant patients and breastfeeding patients.

5.0 Dosage and Administration

The usual adult dosage is 22.5 mg of leuprorelin acetate administered subcutaneously once every 24 weeks. Refer to the Precautions section of the package insert.

6.0 Planned Number of Medical Institutions by Department

Breast surgery and other departments Approximately 60 medical institutions

7.0 Methodology

7.1 Observation Period

24 weeks

7.2 Request to and Contract with the Study Site

This surveillance will be conducted using a Web-based electronic data capture system (CCI). A representative of Takeda Pharmaceutical Company Limited (hereinafter referred to as Takeda's representative) will explain the objectives and contents of the surveillance, operation method of CCI, and handling of electronic signature, user ID, and password to the investigator based on "Request for cooperation for special drug use surveillance," "Implementation outline," "Entry screen image," and "Operation manual of CCI (brief version)" to enter into a written contract with the study site and request the study site to conduct a surveillance within a specified period.

7.3 Method of Patient Registration

Patients will be registered using the central registration method via CCI. After the start of the contract with the study site, the investigator shall register each patient treated with Leuplin PRO by entering patient registration information (refer to Section 9.1) with his/her electronic signature within 14 days after administration of Leuplin PRO (day of administration designated as day 0 and day following the day of administration designated as 1 day post-dose).

7.4 Entry into the (Electronic) Case Report Form and Electronic Signature

The investigator or designee* shall enter patient baseline characteristics and treatment given into CCI with the investigator's electronic signature within approximately 1 month after the end of required observation at 24 weeks after the

start of Leuplin PRO treatment.

For any patient with an adverse event, the investigator or designee shall enter observation results into [CCI] with the investigator's electronic signature after monitoring the patient as long after discontinuation of treatment as possible until the adverse event is confirmed to have resolved or be resolving.

* The investigator's designee should belong to the relevant medical institution (including those under contract with the medical institution such as temporary clinical research coordinators). Before the investigator's designee begins to enter data into [CCI], a physician responsible for the surveillance (one physician per medical institution or department appointed at the time of contract) shall document the designation with the date of designation (no specific style), affix his/her signature or name and seal to the document, and submit it to Takeda's representative.

8.0 Planned Surveillance Period

Surveillance period: From March 2016 to 31 August 2017

Patient registration period: From April 2016 to 28 February 2017^{Note)}

^{Note)} Patient registration (entry into [CCI]) will not be accepted on 1 March 2018 onwards even if Leuplin PRO is administered by 28 February 2018.

If the number of patients enrolled in the surveillance reaches the planned sample size before 28 February 2018, acceptance of registration will be terminated before the end of the patient registration period. If the patient registration period is shortened, the surveillance period will be changed accordingly.

9.0 Surveillance Items

The investigator or designee shall enter the items listed below into [CCI]. The surveillance schedule is presented in Appendix.

9.1 Patient Registration

1) Surveillance items

Date of administration of Leuplin PRO, patient identification number, patient initials, date of birth, assessment based on the exclusion criteria

2) Time points of surveillance

At patient registration

9.2 Patient Baseline Characteristics

1) Surveillance items

Time of diagnosis of premenopausal breast cancer, ECOG Performance Status*, disease status, site of lesions before the start of Leuplin PRO treatment, presence or absence of hormone receptor expression, diagnostic category

(at the start of Leuplin PRO treatment), predisposition to hypersensitivity (presence or absence and details), concurrent illness (presence or absence and details), history of thromboembolism (presence or absence and details), height, body weight, treatment status of premenopausal breast cancer drug immediately before the start of Leuplin PRO treatment (presence or absence and name of the drug)

2) Time points of surveillance

At the start of Leuplin PRO treatment

* ECOG Performance Status

| Score | Definition |
|-------|---|
| 0 | Fully active, able to carry on all pre-disease performance without restriction |
| 1 | Restricted in physically strenuous activity, but ambulatory and able to carry out work of a light or sedentary nature (e.g., light house work, office work) |
| 2 | Ambulatory and capable of all self-care but unable to carry out any work activities; up and about more than 50% of waking hours |
| 3 | Capable of only limited self-care; confined to bed or chair more than 50% of waking hours |
| 4 | Completely disabled; cannot carry on any self-care; totally confined to bed or chair |

(Common Toxicity Criteria, Version 2.0 Published on April 30, 1999. Webpage of the JCOG at <http://www.jco.jp/>)

9.3 Treatment Given

1) Surveillance items

Treatment status of Leuplin PRO (injection site* and full-treatment status of Leuplin PRO*), treatment status of premenopausal breast cancer drug other than Leuplin PRO (presence or absence and name of the drug), presence or absence of and reason for discontinuation of observation

2) Time points of surveillance

Period from the start of Leuplin PRO treatment to 24 weeks after the start of treatment (or discontinuation of observation)

* At the start of Leuplin PRO treatment

9.4 Assessments

1) Assessments

Pregnancy during the observation period (females only)

2) Outcome measure data collection timing

Period from the start of Leuplin PRO treatment to 24 weeks after the start of treatment (or discontinuation of observation)

9.5 Adverse Events (AEs)

1) Surveillance items

Presence or absence of injection site reaction, details of injection site reaction (specific symptom, date of onset, seriousness and reason for seriousness [refer to Table 2]), cause of discontinuation of Leuplin PRO treatment, intervention (presence or absence and contents), date of outcome assessment, outcome, causal relationship to Leuplin PRO [refer to Table 3]).

Presence or absence of AE other than injection site reaction (refer to Table 1), AE term, date of onset, seriousness and reason for seriousness (refer to Table

2), cause of discontinuation of Leuplin PRO treatment, intervention (presence or absence and name of the drug/intervention), date of outcome assessment, outcome, causal relationship to Leuplin PRO* (refer to Table 3)

Patients with “not resolved” or “unknown” outcome or “unevaluable” causal relationship should be followed up wherever possible.

* For the causal relationship to Leuplin PRO, the rationale for “not related” and the reason for “unevaluable” shall be collected.

Note) Additional points to consider for AEs

Abnormal worsening of target disease, for instance, worsening beyond the expected natural course of the disease, will be handled as an AE.

2) Time points of surveillance

Period from the start of Leuplin PRO treatment to 24 weeks after the start of treatment (or discontinuation of observation)

Table 1 Definition of adverse events

An AE is defined as any untoward medical occurrence in a clinical investigation subject administered a drug; it does not necessarily have to have a causal relationship with this treatment. An AE can therefore be any unfavorable or unintended sign (e.g., abnormal laboratory finding), symptom, or disease temporally associated with the use of a drug, whether or not it is considered related to the drug.

The following are also handled as AEs:

- Symptoms and so forth that occur in infants breast-fed by their mothers under treatment with a drug
- Untoward symptoms and so forth that occur in children treated with a drug
- Symptoms and so forth that occur as a result of occupational exposure to a drug
- Symptoms and so forth that occur after administration of counterfeit medicines of our ethical drugs
- Untoward symptoms that have become known to occur in drug users through lawsuits or other legal actions

Table 2 Criteria for assessing seriousness

An AE satisfying any of the following is assessed as serious:

1. Results in death (death)
2. Is life-threatening (risk of death)
3. Requires inpatient hospitalization or prolongation of existing hospitalization (hospitalization/prolonged hospitalization)
4. Results in persistent or significant disability/incapacity (disability)
5. Leads to a congenital anomaly/birth defect (congenital anomaly)
6. Is an important medical event according to 1 to 5 described above, including AEs in Takeda Medically Significant AE List

Takeda Medically Significant AE List

- Acute respiratory failure / acute respiratory distress syndrome (ARDS)
- Anaphylactic shock
- Torsade de pointes / ventricular fibrillation / ventricular tachycardia
- Acute renal failure
- Malignant hypertension
- Pulmonary hypertension
- Convulsive seizures (including convulsions and epilepsy)
- Pulmonary fibrosis (including interstitial pneumonia)
- Agranulocytosis
- Malignant syndrome / malignant hyperthermia

- Aplastic anemia
- Spontaneous abortion / stillbirth and fetal death
- Toxic epidermal necrolysis / mucocutaneous ocular syndrome (Stevens-Johnson syndrome)
- Confirmed or suspected transmission of infectious agent by a medicinal product
- Hepatic necrosis
- Confirmed or suspected endotoxin shock
- Acute liver failure

Table 3 Criteria for assessing the relationship of each adverse event to Leuplin PRO

| Assessment | Criteria for assessment |
|-------------|---|
| Related | An AE that follows a reasonable temporal sequence from administration of a drug (including the course after withdrawal of the drug), or for which possible involvement of the drug can be argued, although factors other than the drug, such as underlying diseases, concurrent illnesses, concomitant drugs, and concomitant treatments, may also be responsible |
| Not related | An AE that does not follow a reasonable temporal sequence from administration of a drug and/or that can reasonably be explained by other factors, such as underlying diseases, concurrent illnesses, concomitant drugs, and concomitant treatments |
| Unevaluable | Information necessary for evaluation, including temporal sequence from administration of a drug (including the course after withdrawal of the drug), underlying diseases, concurrent illnesses, concomitant drugs, and concomitant treatments, is not sufficient. |

